## 1.3. Treatment Groups

The treatment groups are Safety Run-in (JNJ-63723283+daratumumab); and Arm A (daratumumab alone) and Arm B (JNJ-63723283+ daratumumab) for Part 2.

## 1.4. End of Follow-up and Duration of Follow-up

The end of follow-up is the date of death for subjects who died. For those who are still alive, the end of follow-up is defined as the maximum date of the following study evaluations: labs (hematology, chemistry, serology, coagulation, thyroid function ), adverse events, vital signs, ECOG performance status, study drug administration, 12-lead ECG, pre-infusion medications, post-infusion medications, concomitant medications, subsequent anti-cancer treatment, tumor assessment, clinical events/disease response per investigator and date of last known to be alive.

Duration of follow-up (in months) equals the end of follow-up minus the first dosing date plus 1 for Part 1 and equals the end of follow-up minus the randomization date plus 1 for Part 2, divided by 365.25/12.

Study duration of follow-up will be summarized by treatment group and overall for safety Analysis Set.

## 1.5. Subject information

The distribution of subjects by region and country will be presented for safety analysis set by treatment group and overall.

• **Demographics and baseline characteristics:** Demographics and baseline characteristics will be summarized for safety analysis set by treatment group and overall. A listing of subject demographic and baseline characteristics will be provided as well. Table 1 and Table 2

respectively present a list of the demographic variables and baseline disease characteristics that will be summarized by treatment group and overall.

### **Table 1: Demographic Variables**

Continuous Variables:	Summary Type		
Age (years)	Descriptive statistics (N, mean,		
Weight (kg)	standard deviation [STD], median		
Height (cm)	and range [minimum and maximum]).		
Categorical Variables			
Age (<65 years, $\geq$ 65 years and <75 years, $\geq$ 75 years)			
Weight (≤65kg, >65kg and ≤85kg, >85kg)			
Sex (male, female)	N fraguency distribution with the		
Race (American Indian or Alaska Native, Asian, Black or African	N, frequency distribution with the number and percentage of		
American, Native Hawaiian or other Pacific Islander, White,	subjects in each category.		
Multiple a , not reported)	subjects in each category.		
Ethnicity (Hispanic or Latino, not Hispanic or Latino, not reported)			
Baseline ECOG (0, 1, 2)			

a If multiple race categories are indicated, the Race is recorded as 'Multiple'

### **Table 2: Baseline Disease Characteristics**

Continuous Variables:	Summary Type
Time since MM diagnosis (years)	Descriptive statistics (N, mean,
	standard deviation [STD], median and range [minimum and
	maximum]).
Categorical Variables	3/
Type of multiple myeloma (IgG, IgA, IgM, IgD, IgE, light	
chain only [kappa and lambda], biclonal, negative	
immunofixation, not detected)	
Type of measurable disease (serum measurable only [IgG, IgA	
and Other], both serum and urine measurable, urine measurable	
only, serum FLC measurable)	
ISS staging at screening by central laboratory assessment (I, II,	
III)	N, frequency distribution with the
Number of lytic bone lesions (None, 1-3, 4-10, more than	number and percentage of subjects
10)	in each category.
Presence of diffuse myeloma-related osteopenia (Yes, No)	
Number of extramedullary plasmacytomas $(0, \geq 1)$	
Bone marrow % plasma cells ( $<10, 10 - 30, >30$ )	
Status of cytogenetic abnormality (standard-risk, high-risk	
[Del17p, T(4;14), T(14;16)] ),	
ECG overall conclusion (normal, abnormal [clinically	
significant, not clinically significant, not evaluable)	

• **Subject Disposition:** The number of subjects in the following disposition categories will be summarized throughout the study for safety population by treatment group and overall: subjects who discontinued study treatment, reasons for discontinuation of study treatment, subjects who terminated study prematurely, and reasons for termination of study. Listings of subjects will be provided for the following categories: subjects who discontinued study treatment, and subjects who terminated study prematurely.

- **Medical history:** Medical history collected at baseline or screening visit will be summarized by system-organ class and preferred term for each treatment group and overall.
- **Prior and concomitant medication:** Summaries of concomitant medications will be presented by therapeutic class, pharmacologic class and preferred term by treatment group and overall for safety population. A summary of prior therapies (systemic therapy, radiotherapy, or cancer-related surgery/ procedure) will be provided by treatment group. Specifically, the number of prior lines of therapy will be calculated according to IWMG consensus guidelines (Durie 2006; Kumar 2016; Rajkumar 2011) and summarized by the following categories:  $\leq 3$  and > 3 through frequency and descriptive statistics. Subjects with prior cancer-related surgery/procedure and with prior radiotherapy will be listed for safety population.
- **Pre-infusion and post-infusion medication:** Pre-infusion and post-infusion medication will be summarized by therapeutic class, pharmacologic class and preferred term by treatment group and overall for safety population. A listing will be provided for pre-infusion medication and post-infusion medication, respectively.
- Exposure: Summary of treatment exposure will be provided for safety population. The total number of treatment cycles received for each subject will be summarized by frequency and descriptive statistics (N, mean [SD], median, range [minimum, maximum]) by treatment group. Descriptive statistics for duration of study treatment, defined as (date of last dose of study treatment date of first dose of study treatment) +1, will be presented by treatment group. Subject-month of exposure are calculated as days of duration/365.25\*12. Total number of daratumumab and JNJ-63723283 infusions will be calculated. respectively. Exposure will be listed for safety population.

The number and percentage of subjects with treatment cycle delay will be calculated by treatment group. The frequencies of actions planned prior to infusion start (infusion delayed, infusion skipped or study drug permanently discontinued) and taken during infusion (infusion interrupted, infusion rate decrease, infusion aborted) will be summarized, together with reasons reported (adverse events or other) accordingly.

Descriptive statistics will be presented for the following parameters: dose and relative dose intensity of daratumumab, dose and relative dose intensity of JNJ-63723283.

• **Protocol deviation:** A listing of subjects with major protocol deviations including treatment group, subject ID, type of deviation, and reasons for deviation will be provided.

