#### Figure 1: Study Scheme

## Part 1: Safety Run-in Phase

A 6-subject Safety Run-in cohort will be evaluated by the Safety Evaluation Team (SET; see Section 3.2) to determine the safety and tolerability of JNJ-63723283 in combination with daratumumab before the start of the randomized phase of Part 2 of the study. The DLT evaluation period for the Safety Run-in cohort will be 1 cycle (28-days).

- Study drug administration:
  - Daratumumab: Daratumumab 16 mg/kg IV will be administered once every week (Weeks 1 to 8); then once every other week for 16 weeks (Weeks 9 to 24); then once every 4 weeks (Week 25 onwards).
  - JNJ-63723283: 240 mg IV (fixed dose) will be administered during Week 1 on Cycle 1 Day 2, Cycle 1 Day 15, then every 2 weeks thereafter.
  - Daratumumab will be administered prior to administration of JNJ-63723283. Subjects will continue to receive study treatment until confirmed disease progression, unacceptable toxicity, or any other treatment discontinuation criteria are met.
- If <2 of the first 6 DLT evaluable subjects experience a dose-limiting toxicity (DLT; see Section 3.2) during the first treatment cycle (ie, 28 days), the selected doses and dose regimens for JNJ-63723283+daratumumab combination therapy will be considered tolerable, and the study will proceed to the Part 2 randomized phase after the SET provides approval.
- If ≥2 subjects experience a DLT during the first treatment cycle (ie, 28 days), new subject enrollment into the Safety Run-in cohort will stop until after the SET convenes to review DLT data from those subjects and makes recommendations regarding the conduct of the study. The SET may consider the exploration of alternate doses and dose regimens, in an additional safety run-in cohort.
- Subjects in the Safety Run-in cohort may continue to receive additional cycles of JNJ-63723283+daratumumab while enrollment into the Safety Run-in cohort is ongoing and after the study has proceeded to the randomized phase until they meet protocol-specified discontinuation criteria. Subjects who experience unacceptable toxicity directly attributable to JNJ-63723283 may be eligible to receive daratumumab alone, after consultation with the Sponsor.

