## **Adverse Events**

The verbatim terms used in the CRF by investigators to identify adverse events will be coded using the Medical Dictionary for Regulatory Activities (MedDRA). Treatment-emergent adverse events are adverse events with onset during the treatment phase or that are a consequence of a pre-existing condition that has worsened since baseline. All reported adverse events will be included in the analysis. For each adverse event, the percentage of subjects who experience at least 1 occurrence of the given event will be summarized by treatment group. In addition, comparisons between treatment groups will be provided if appropriate.

Summaries, listings, datasets, or subject narratives may be provided, as appropriate, for those subjects who die, who discontinue treatment due to an adverse event, or who experience a severe or a serious adverse event.

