#### **Daratumumab Monotherapy Period:**

Data collection will be limited to SAE reporting into the Sponsor's global safety database.

No data will be entered in eCRF once Protocol Amendment 2 is implemented at a site. Once Protocol Amendment 2 is implemented at all sites, clinical database can be locked.

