## 1. ANALYSIS DETAILS

This document contains definitions of analysis sets, derived variables and planned data presentation specifications which will be used in clinical study report of study 54767414MMY2036. The analysis will be performed after final data base lock when protocol 54767414MMY2036, Amendment 2 is approved and implemented at all sites.

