## 1.1. Overview of Study Design

This is a randomized, open-label, multicenter, multiphase study assessing the efficacy and safety of JNJ-63723283 (an anti-PD-1 monoclonal antibody) in combination with daratumumab compared with daratumumab alone in subjects with multiple myeloma who have received at least 3 prior lines of therapy including a PI and an IMiD or whose disease is double refractory to both a PI and an IMiD. A diagram of the study design is provided in Figure 1.

As of 25 May 2018, the Sponsor terminated further enrollment into this study and subjects in Screening were deemed Screen Failures and were not further randomized into the study. Subjects continuing on study will receive daratumumab monotherapy starting 25 May 2018. Part 3 is no longer applicable for this study.

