## 1.7. Safety

### • Adverse events:

- An overview of treatment-emergent adverse events (TEAEs) will be summarized for safety population by treatment group and overall.
- Incidence of TEAEs will be summarized by MedDRA SOC, and preferred term.
- List of subjects with any TEAEs, serious TEAEs, toxicity grade 3 or 4 TEAEs, treatmentemergent Infusion Related Reactions (IRRs), and immune-mediated TEAEs will be provided for safety population.
- List of subjects with any TEAEs leading to all treatment discontinuation, TEAEs leading to any treatment discontinuation, TEAEs with outcome death, TEAEs leading to cycle delay or dose modifications, and TEAEs leading to infusion interrupted, infusion rate decreased or infusion aborted will be provided for safety population.
- Subjects who died during the study, and had new malignancies will also be listed, respectively.
- Laboratory values: Laboratory values will be listed at each time points for safety analysis set.
  - The hematology parameters include: hemoglobin, lymphocytes, neutrophils, platelet, and white blood cell (WBC).
  - The chemistry parameters include: alanine aminotransferase (ALT), alkaline phosphatase, aspartate aminotransferase (AST), amylase, calcium, creatinine, creatinine clearance, potassium, sodium, total bilirubin, and total lipase,
  - The thyroid function parameters include: free thyroxine, free triiodothyronine, thyroid stimulating hormone, and total triiodothyronine.
- Electrocardiograms (ECG): ECG values will be reported at each time points for safety analysis set in listings.
- Vital signs: Vital signs will be listed at each time points for safety analysis set. The variables include: weight, blood pressure (systolic and diastolic).

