# TSIEX-ST01: Summary of Treatment Cycles, Duration of Study Treatment and Dose Intensity; Safety Analysis Set (Study 54767414MMY2036)

Dose intensity for JNJ-63723283 (mg/cycle) b			
N	###	###	###
Mean (SD)	xx.x (xx.xx)	xx.x (xx.xx)	xx.x (xx.xx)
Median	XX.X	XX.X	XX.X
Range	(xx;xx)	(xx;xx)	(xx;xx)
Relative dose intensity for JNJ-63723283 (%)			
N	####	###	###
Mean (SD)	xx.x (xx.xx)	xx.x (xx.xx)	xx.x (xx.xx)
Median	XX.X	XX.X	XX.X
Range	(xx;xx)	(xx;xx)	(xx;xx)

a Dose intensity (mg/kg/cycle) is calculated as the sum of total doses (mg/kg) received in all cycles divided by the number of treatment cycles on daratumumab.

b Dose intensity (mg/cycle) is calculated as the sum of total doses (mg) received in all cycles divided by the number of treatment cycles on JNJ-63723283.

Note: The relative dose intensity (%) is the ratio of total actually received dose and total planned dose.

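### Does one joint treatment duration, with TEAEs not marked by the last JNJ-63723283 dose, misstate combination exposure and safety in the Safety Run-in?

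*SAP*

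**What the plan says.** **Duration.** SAP Section 1.5 (Exposure) gives "duration of study treatment, defined as (date of last dose of study treatment" less the date of first dose, plus one day, converted to months by dividing by 365.25 and multiplying by 12. The TSIEX-ST01 mock for TSIEXP01 has one duration block and one cycle-count block. Infusions, total dose, dose intensity and relative dose intensity are shown for each drug, and a footnote states that "The relative dose intensity (%) is the ratio of total actually received dose and total planned dose".

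**Adverse events.** Protocol Section 11.10: "Treatment-emergent adverse events are adverse events with onset during the treatment phase". The window is not tied to either drug. SAP Section 1.7: "An overview of treatment-emergent adverse events (TEAEs) will be summarized for safety population by treatment group and overall". TSFAE01 has rows for relatedness to each drug and for discontinuation of each drug. LSFAE01 lists onset date and study day, with relationship and action taken for each drug. Neither these outputs nor TSFAE02 refer to the last JNJ-63723283 dose.

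**How daratumumab-only time arises.** SAP Section 1.1: "Subjects continuing on study will receive daratumumab monotherapy starting 25 May 2018". Protocol Section 3.1, for the run-in: "Subjects who experience unacceptable toxicity directly attributable to JNJ-63723283 may be eligible to receive daratumumab alone, after consultation with the Sponsor".

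**When the data end.** Protocol Section 17.5: "No data will be entered in eCRF once Protocol Amendment 2 is implemented at a site". The SAP analysis follows final database lock, once "Amendment 2 is approved and implemented at all sites" (SAP Section 1).

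**The concern.** SAP Section 1.3 labels the Safety Run-in as JNJ-63723283 plus daratumumab throughout. The primary objective of Part 1 is the safety of that combination. A run-in subject who stopped JNJ-63723283, for toxicity or at the sponsor's stop, and stayed on daratumumab keeps adding to the joint duration and the cycle count. A TEAE starting in that period is counted under the combination label. TSIEXP01, TSFAE01 and TSFAE02 are all marked for the report text, so a reader might take the duration as time on both drugs and every TEAE as one that began on both.

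Two further doubts follow. Non-serious events are not reported in the Daratumumab Monotherapy Period (Protocol Section 12.3.1.1), so capture might differ before and after the switch. And if planned JNJ-63723283 dose went on accruing after the stop, a sponsor decision would look like missed doses in the relative dose intensity.

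**Working it through.** The plan states no figure for this point, so there is none to reproduce. The check is how far the joint duration can exceed time on the combination, and whether other planned outputs show the difference.

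**1. Size of the possible excess**

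- Joint duration = last dose of any study drug − first dose + 1.
- Time on the combination, on the same footing = last JNJ-63723283 dose − first dose + 1.
- Excess = last daratumumab dose − last JNJ-63723283 dose.
- One month = 365.25/12 = 30.4375 days.

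From 25 May 2018 to the Amendment 2 date, 20 June 2018, is 6 + 20 = 26 days, or 26/30.4375 = 0.85 month. eCRF entry stayed open at least that long. An individual subject's excess can still be zero, because continuing was optional. The documents give no dosing, site-implementation or lock dates, so the days on the combination below are assumptions. The 105-day gap, to the SAP amendment of 07 Sep 2018, is an assumed long case and not a known cut-off. Share = gap/(combination days + gap).

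| Days on combination (assumed) | Gap 26 days | Gap 105 days |
|---|---|---|
| 28 | 26/54 = 48.1% | 105/133 = 78.9% |
| 56 | 26/82 = 31.7% | 105/161 = 65.2% |
| 112 | 26/138 = 18.8% | 105/217 = 48.4% |
| 168 | 26/194 = 13.4% | 105/273 = 38.5% |

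Example: 112 + 26 = 138 days is reported as 138/30.4375 = 4.53 months, of which 112/30.4375 = 3.68 months are on the combination. The share can be large for a given subject, so the conclusion cannot rest on it being small.

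**2. Whether TSIEXP01 already shows JNJ-63723283 time**

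JNJ-63723283 is a fixed 240 mg every 2 weeks, two infusions per 28-day cycle (Protocol Table 8 and Section 3.1). In the example, 112 days is 112/28 = 4 cycles, or 8 infusions and 8 × 240 = 1,920 mg. Read back, 8 infusions × 14 days = 112 days = 3.68 months. Infusion count and total dose therefore track time on JNJ-63723283, apart from delayed or skipped doses, which TSIEXP02 summarises. The dose-intensity footnote divides by cycles on JNJ-63723283, so cycles on that drug are derived in any case.

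**3. Whether the periods can be separated for each subject**

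| Question | Planned output |
|---|---|
| When was each drug given? | LSIEX01: infusion dates by subject and drug |
| When did each TEAE begin? | LSFAE01: onset date and study day |
| Was JNJ-63723283 withdrawn for the event? | LSFAE01: action taken for each drug |
| Was it immune-mediated, or a DLT? | LSFAE01: a column for each |
| When was each drug last given before a death? | LSFDTH01: study day of last infusion for each drug |

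The run-in is planned at about 6 subjects. Protocol Section 11.12 says the number treated is small, drops formal testing and has safety data listed by subject. Reading the listings is the planned analysis.

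**4. Whether any planned result would be wrong**

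The duration is titled as study treatment, and for that it is right. The TEAE tables count events under the assigned group; moving events after the last JNJ-63723283 dose elsewhere would take late immune events out of the group that received the drug. No exposure-adjusted event rate is planned, so the joint duration is not a denominator for any safety estimate. The DLT window is the first 28 days (Protocol Sections 3.1 and 3.2). Arm A columns in the SAP layouts imply that the run-in review was complete before the May 2018 switch, though that is an inference.

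**5. Planned dose**

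Protocol Sections 1.4 and 3.1 discontinue the combination, so no JNJ-63723283 dose is planned after the stop. Nothing in the SAP makes planned dose accrue beyond it. SAP Section 8 sends further rules to a separate document that is not available here.

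**The case for a change.** The best argument for a change is that the report text should stand on its own. Every other exposure measure that can be split by drug is split in TSIEXP01; duration is the exception. The early-toxicity route to daratumumab alone does not depend on the termination, so mixed time was foreseeable. Two duration rows, a TEAE row and a listing column would cost little, and the last-dose date for each drug is already needed for LSFDTH01.

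The facts behind this stand: there is one duration, there is no onset marker, and daratumumab-only time can enter. The inference does not. The additions would re-display information that the plan already produces and would alter no existing count or summary. A TEAE row split at the last JNJ-63723283 dose would hold very small counts in a cohort of about 6.

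The capture point also weakens on inspection. If the monotherapy reporting rule applied from 25 May 2018, few later non-serious events would reach the tables. If it applied only from site implementation, capture was normal until eCRF entry closed. Heavy mixing and badly incomplete capture are unlikely together.

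**Conclusion.** No change to the plan is needed. Safety Run-in summaries can include daratumumab-only time of unknown and possibly zero amount: 13% to 48% of the joint duration for a 26-day gap after 168 to 28 days on the combination, and more if the gap was longer. Those figures rest on assumed dosing dates. The conclusion does not depend on them, because the reported duration and TEAE counts are correct for what they are labelled, and JNJ-63723283 exposure is visible in TSIEXP01 and dated in LSIEX01. The end point of planned JNJ-63723283 dose is a detail that analysts would set sensibly at the sponsor's stop. A duration row for each drug, or a listing column for days since the last JNJ-63723283 dose, would be a convenience for readers and could be added at the programmers' discretion.

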## 1.6. Efficacy

A listing of subjects' best response, and disease progressions based on investigator's assessment, and overall survival will be provided for the safety analysis set, including treatment group, subject ID, and baseline measurable disease type. For subjects who had progression disease (PD), the PD reasons based on investigator's assessment will be listed.

## 1.7. Safety

### • Adverse events:

- An overview of treatment-emergent adverse events (TEAEs) will be summarized for safety population by treatment group and overall.
- Incidence of TEAEs will be summarized by MedDRA SOC, and preferred term.
- List of subjects with any TEAEs, serious TEAEs, toxicity grade 3 or 4 TEAEs, treatmentemergent Infusion Related Reactions (IRRs), and immune-mediated TEAEs will be provided for safety population.
- List of subjects with any TEAEs leading to all treatment discontinuation, TEAEs leading to any treatment discontinuation, TEAEs with outcome death, TEAEs leading to cycle delay or dose modifications, and TEAEs leading to infusion interrupted, infusion rate decreased or infusion aborted will be provided for safety population.
- Subjects who died during the study, and had new malignancies will also be listed, respectively.
- Laboratory values: Laboratory values will be listed at each time points for safety analysis set.
  - The hematology parameters include: hemoglobin, lymphocytes, neutrophils, platelet, and white blood cell (WBC).
  - The chemistry parameters include: alanine aminotransferase (ALT), alkaline phosphatase, aspartate aminotransferase (AST), amylase, calcium, creatinine, creatinine clearance, potassium, sodium, total bilirubin, and total lipase,
  - The thyroid function parameters include: free thyroxine, free triiodothyronine, thyroid stimulating hormone, and total triiodothyronine.
- Electrocardiograms (ECG): ECG values will be reported at each time points for safety analysis set in listings.
- Vital signs: Vital signs will be listed at each time points for safety analysis set. The variables include: weight, blood pressure (systolic and diastolic).

